5.1.1.5.3 Vital Signs

Vital signs will be summarized in total for the Safety Population as follows:

Table 5-14 Vital Signs Summaries

Endpoint	Description	Timing	Methodology
Descriptives	Summary by parameter and analysis visit	Screening (visit 1),	CFB ¹ descriptives
_	 Parameters specified in Table 6-7 	Week 12/early exit	_

¹ The measurement at the screening (visit 1) will be determined using the latest pre-dose measurement on or before day 1.

5.1.1.5.4 Local Dermal Tolerability

The local tolerability examination of the face is to be performed by the investigator (or appropriately trained designee), who will assess dryness, scaling, and erythema, and the patient will assess stinging/burning. The assessor will examine the skin area where study drug is applied in comparison to the surrounding skin from day 1 to week 12. The same assessor will rate dryness, scaling, and erythema at each visit, where possible. Local tolerability signs and symptoms will be rated using a severity scoring of 0 (none), 1 (mild), 2 (moderate), or 3 (severe), as further defined in Table 6-8.

Local dermal tolerability data will be summarized in total and by cohort (PK cohort and Non-PK cohort) for the Safety Population as follows:

Table 5-15 Local Dermal Tolerability Summaries

Endpoint	Description	Timing	Methodology
Descriptives ¹	Summary by parameter and analysis visit	Pre-dose on baseline	Categorical
	• Parameters specified in Table 6-8.	(day1), post-dose on	Descriptives
		baseline (day 1),	
		Weeks 1, 2, 4, 8,	
		and 12/early exit	

¹ All local dermal tolerability data will be listed.

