## **2. Study Objectives and Clinical Hypotheses**

### **2.1 Study Objectives**

To evaluate the safety and tolerability of ACZONE 7.5% administered topically once-daily for 12 weeks in 9 to 11 year-olds with acne vulgaris.

To evaluate the peak and trough plasma drug concentrations in 9 to 11 year-olds with acne vulgaris following once-daily dosing of ACZONE 7.5% under maximal use conditions for the first 8 days (+ 2 days).

To explore the efficacy of ACZONE 7.5% administered topically once-daily in 9 to 11 year-olds with acne vulgaris.

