**Table 3 Investigator's Global Assessment**

Grade		Description
0	Clear	
 
No comedones, papules or pustules
 
Residual hyperpigmentation and erythema may be present
 

1	Almost Clear	
 
Rare comedones
 
No more than a few small papules and pustules
 

2	Mild	
 
Easily recognizable comedones in limited numbers
 
+/- Presence of small papules and pustules
 

3	Moderate	
 
Many comedones
 
+/- Easily recognizable small and medium-sized papules
 
No nodules or cysts.
 

4	Severe	
 
Widespread and numerous comedones
 
Many small, medium-sized and large papules and pustules
 
Nodules or cysts may or may not be present.
 

(Eichenfield et al, 2013, J of Dermatol)

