### 7.3.1 Safety Analyses

Safety variables are treatment-emergent adverse events (TEAEs), including new findings from physical examinations, local (dermal) tolerability, and vital signs.

All adverse events will be coded from the verbatim text to the lower level term and mapped to preferred term (PT) and primary system organ class (SOC) using the Medical Dictionary for Regulatory Activities (MedDRA).

All TEAEs will be listed by patient. For TEAEs regardless of causality, and for treatment-related TEAEs, the number and percentage of patients reporting the TEAEs at least once will be tabulated by descending order of incidence rate by PT within primary SOC, and by primary SOC, PT, and severity.

Local (dermal) tolerability data will be summarized using descriptive statistics and frequency distributions. Vital signs will be summarized using descriptive statistics. Positive pregnancy test results will be listed.

More detailed analyses for the safety measures will be described in the analysis plan.

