4.1 Study Design Summary

Structure: Multicenter, open-label, non-comparative trial

Duration: Patient participation is up to approximately 16 weeks from screening to trial exit;

treatment duration is up to 12 weeks

Study Treatment Groups: ACZONE 7.5%

Controls: No control group

Dosage/Dose Regimen: All patients will receive treatment with ACZONE 7.5% once-daily Pharmacokinetic (PK) Cohort (at least 16 evaluable PK patients): For the first 8 days (+ 2 days), study drug will be administered once-daily under maximal use condition (~2 grams/day) to the entire face, neck, upper chest, upper back and shoulders as instructed by the study site. The study drug should be rubbed in gently and completely. On Day 1, the study drug will be administered on site. From Day 2 through Day 7, the study drug will be administered in the morning at home by the patient's legally authorized representative. At the Week 1/Visit 3 [Day 8 (+2 days)], the study drug will be administered on site in the morning. After the Week 1/Visit 3, patients or the patient's legally authorized representative will apply a pea-sized amount of study drug in a thin layer to the patient's face, once-daily, at home for the remaining 11 weeks, the same as the dose regimen for the Non-PK Cohort. Acne-affected areas on the upper chest, upper back, and shoulders should also be treated with a thin layer during the final 11 weeks. Evaluable PK patients are defined as those that are administered at least 8 days of study drug under maximal use conditions, and provided PK samples for analysis without any major protocol deviations.

Non-PK Cohort (approximately 84 patients): Patients or the patient's legally authorized representative will apply a pea-sized amount of study drug in a thin layer to the patient's face

once-daily for 12 weeks as instructed by the study site. Acne-affected areas on the upper chest, upper back, and shoulders should also be treated with a thin layer.

Randomization/Stratification: No randomization; all patients will receive ACZONE 7.5%. Assignment to PK or Non-PK Cohort will be based on patient/legally authorized representative choice and investigator's judgment.

Visit Schedule: up to 7 scheduled study visits (see Table 4-2 for further details):

- Visit 1: Screening (-30 to day -1)
- Visit 2: Day 1 (Baseline)^a
- Visit 3: Week 1 (Day 8 + 2 days)
- Visit 4: Week 2 (±3 days)
- Visits 5 and 6: Weeks 4 and 8 (\pm 7 days)
- Visit 7: Week 12 / Early Exit (±7 days)

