5.1.1.1.3 Statistical Methodology

The methodologies defined below apply as specified to individual endpoints defined in this SAP.

Table 5-2 Statistical Methodology

Methodology	Description		
Categorical counts	Number of participants in individual categories		
	 ○ Participants with ≥ 1 qualifying event counted once per individual category 		
Categorical	Number and percentage of participants in individual categories		
descriptives	 ○ Participants with ≥ 1 qualifying event counted once per individual category 		
	• N1 if percentage denominator ≠ number of participants in the population (standard		
	percentage denominator)		
	 N1 = participants with non-missing baseline value 		

Methodology	Description			
Continuous	N1, mean, standard deviation (SD), median, minimum, maximum			
descriptives	• N1 = participants with non-missing value			
CFB ¹ descriptives	 Continuous descriptives for baseline, postbaseline, and change from baseline (CFB) values N1 = participants with non-missing values at both baseline and the specified postbaseline analysis visit 			

¹CFB = change from baseline

Raw and derived data listings will be provided, and will be fully defined in the table, figure, and data listing specification document.

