6.2 Analysis Visit Windows

Unless otherwise specified, if there are multiple valid measurements within the same analysis window, the one closest to the target day of the visit will be used. If multiple valid scores are equidistant from the target day of the visit, the latter observation will be used to represent the analysis window. All assessments will be included in respective listings.

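### SAP Table 5-15 tabulates local tolerability only as grades at each visit, so it cannot show how many children worsened from their own Day 1 pre-dose grade

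*SAP*

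**What the plan says.** Tolerability belongs to the first-listed objective in Protocol 2.1: "To evaluate the safety and tolerability of ACZONE 7.5% administered topically once-daily for 12 weeks in 9 to 11 year-olds with acne vulgaris". The SAP design summary (4.1) states "Controls: No control group". Dryness, scaling, erythema and stinging/burning are each graded 0 to 3 on the face, before and after dosing on Day 1 and at Weeks 1, 2, 4, 8 and 12/early exit.

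The planned analysis is brief. Protocol 7.3.1 says "Local (dermal) tolerability data will be summarized using descriptive statistics and frequency distributions" and leaves further detail to the analysis plan. SAP 5.1.1.5.4 says "Local dermal tolerability data will be summarized in total and by cohort (PK cohort and Non-PK cohort) for the Safety Population as follows". The single entry in Table 5-15 is "Summary by parameter and analysis visit", using the categorical method, which Table 5-2 defines as "Number and percentage of participants in individual categories". A footnote adds that all tolerability ratings will be listed. Neither document plans a shift from the pre-dose grade, a count of children who worsened, or a worst post-dose grade per child.

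On visit windows, SAP 6.2 says that "if there are multiple valid measurements within the same analysis window, the one closest to the target day of the visit will be used".

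**The concern.** Without a comparator, the pre-dose rating is the only thing that separates a sign the child already had from one that appeared on treatment. Table 5-15 uses it as one more row. Two rows of grade counts give the net movement between visits: children who newly developed a sign minus children in whom it resolved. They do not give either part.

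The SAP follows the within-patient principle elsewhere. Lesion counts and vital signs get change from baseline. Adverse events get a treatment-emergent definition that includes worsening, and a worst-severity tabulation. Local tolerability, which is named in the first objective, gets neither.

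At stake is the figure a reader would want for the hypothesis in Protocol 2.2 that the gel is well tolerated: the proportion of children whose skin became worse than before the first dose.

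**Working it through.** **Inputs.** Protocol 4.1 plans about 100 children with 15% attrition: 100 × (1 − 0.15) = 85, which reproduces the stated figure of about 85 completers. The documents give no tolerability rates, so every rate below is an assumption. For simplicity both rows are taken over the same 85 children.

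**What two rows can tell.** Let *a* be the number with any grade of the sign pre-dose and *b* the number at Week 12, out of *N*. The number newly affected from grade 0 is at least max(0, *b* − *a*) and at most min(*b*, *N* − *a*). Counts are rounded to whole children.

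| Assumed pre-dose → Week 12 | a | b | Newly affected, range |
|---|---|---|---|
| 20% → 10% | 17 | 8 | 0 to 8 (0–9%) |
| 30% → 20% | 26 | 17 | 0 to 17 (0–20%) |
| 40% → 25% | 34 | 21 | 0 to 21 (0–25%) |
| 40% → 40% | 34 | 34 | 0 to 34 (0–40%) |
| 2% → 10% | 2 | 8 | 6 to 8 (7–9%) |

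For 40% → 25%: max(0, 21 − 34) = 0; min(21, 85 − 34) = 21; 21/85 = 24.7%.

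The full four-grade table does not help. With grades 0/1/2/3 moving from 51/21/11/2 to 64/14/6/1, a linear programme over all cross-tabulations with those margins allows 0 to 21 children to have worsened. With a sign rare before dosing, 83/2/0/0 moving to 75/8/2/0, the range is 8 to 10.

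**Direction.** Suppose 40% have erythema pre-dose, half of these resolve, and 30% of the other 60% develop it. The later row reads 0.40 × 0.5 + 0.60 × 0.30 = 0.38, a fall of 2 points, while 0.60 × 0.30 = 18% are newly affected. Varying baseline prevalence over 20–60%, resolution over 30–50% and emergence over 10–30%, the net change runs from −26 to +18 points while 4–24% are newly affected. Read as a change, the row understates emergence by the children who resolved; read as a level, it overstates emergence by those in whom the sign persisted.

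**Ever affected.** If 5% of children are affected at each of the five visits after Day 1, the share ever affected is 5% if they are always the same children, 1 − 0.95⁵ = 22.6% if visits are independent, and 5 × 5% = 25% if no child is affected twice. The by-visit rows are the same in all three cases.

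**Windows.** In SAP Table 6-3 the Week 4 window is Days 22 to 42, with target Day 29. A child rated on Day 29 who exits on Day 36 has both ratings in that window. The Day 29 rating is 0 days from target and the Day 36 rating is 7, so the exit rating is not used. Table 5-15 labels its last row Week 12/early exit, but the Week 12 window opens at Day 71, and the SAP does not say that an earlier exit rating goes there regardless. Unscheduled ratings on Days 2 to 5 fall in no window.

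**The case against.** The strongest reply is that the adverse event tables already do much of this. Protocol 6.3.4 records any sign the investigator judges to be an adverse event, and Protocol 12.1 requires it for clinically significant signs. SAP Tables 5-12 and 5-13 then count each child once by worst severity, in total and by cohort, and count worsening of a pre-treatment event as treatment-emergent. That stands, and it confines the gap to worsening not judged an adverse event. Those ratings are in the listing, but a listing gives no rate.

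A reader might infer that the table is biased toward good tolerability. The documents do not support that: the net change can go either way, and the SAP sets no tolerability threshold or decision rule.

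A reader might also take common baseline redness as established. It is not. The IGA line "Residual hyperpigmentation and erythema may be present" describes grade 0 only, while entry requires grade 2 to 4. Protocol 1.3 describes preadolescent acne as mostly mild, noninflammatory and often untreated, which also weakens any argument from recently stopped topical treatments. Papules are defined as red (Protocol 6.2.2), so erythema before dosing is plausible, but its frequency is unknown. Nor should the argument be stretched to all four signs alike. Stinging/burning is defined as a sensation after dosing, so little of it would be expected pre-dose.

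Two further points stand. The worst of several post-dose ratings set against one pre-dose rating will show some worsening through ordinary fluctuation, and without a control it cannot be attributed to the gel. The table specifications are in a separate document not seen here and might contain more, although the SAP text that defines the analyses does not.

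**Conclusion.** The point holds in a limited form. Table 5-15 cannot give the number of children who worsened from their own pre-dose grade when that grade is often non-zero, which chiefly concerns erythema. Under the assumed fall from 40% to 25% in 85 children, the uncertainty is 0 to 21 children. With an assumed 2% pre-dose it shrinks to 6 to 8, and the by-visit row is nearly enough for that visit. The size therefore rests on baseline prevalence, which the documents do not give. What is missing is a tabulated rate for worsening not judged an adverse event. Separately, the closest-to-target rule can drop an early-exit or unscheduled rating from the only tolerability table.

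**What to change.** In SAP Table 5-15 add, for each of the four parameters, in total and by cohort:

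1. A shift table from the Day 1 pre-dose grade to each visit, with the number and percentage worsened by at least one grade. Name the pre-dose record explicitly as baseline: Table 6-3 defines the safety baseline by treatment day alone, whereas the efficacy baseline in Table 6-2 carries a pre-dose condition.
2. The worst post-dose grade per child over all post-dose ratings, including early-exit and unscheduled ones, cross-tabulated with the pre-dose grade.

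Report both beside the by-visit distribution, not in place of it. The cost is SAP wording and two more descriptive tables; no new data are needed. The worst-grade table should carry a note that ordinary fluctuation inflates it somewhat and that it cannot by itself attribute worsening to the drug.

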5.1.1.5.5 Urine Pregnancy Test

All patients with positive pregnancy test results will be listed.

5.1.1.6 Subgroup Analyses

No subgroup analyses are planned for this study.

5.1.1.7 Interim Analyses

No interim analyses are planned for this study.

5.1.2 Determination of Sample Size

The sample size for the trial was determined empirically, and is consistent with that requested by the FDA in the post-marketing requirement for ACZONE 7.5%.

5.2 Changes in the Conduct of the Study or Planned Analyses

5.2.1 Changes in the Conduct of the Study

Not applicable.

5.2.2 Changes to Analyses Prior to Database Lock

Not applicable.

6. Data Handling and Analysis Conventions

6.1 Study Treatment Conventions

6.1.1 Analysis Days

Treatment days are defined as follows:

Table 6-1 Analysis Day Definitions

Term	Description
Treatment Day	Relative to treatment start date
	If analysis date ≥ treatment start date:
	 Day = analysis date - treatment start date + 1
 Day 1 = treatment start date 	
If analysis date < treatment start date:	
	 Day = analysis date - treatment start date
	 Day -1 = day before treatment start date
	o There is no Day 0

6.2 Analysis Visit Windows

Unless otherwise specified, if there are multiple valid measurements within the same analysis window, the one closest to the target day of the visit will be used. If multiple valid scores are equidistant from the target day of the visit, the latter observation will be used to represent the analysis window. All assessments will be included in respective listings.

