### **6.3.3 Unscheduled Visits**

If a patient is seen for an unscheduled visit, an assessment and record of adverse events should be completed. Additional evaluations should be performed as necessary, and the appropriate eCRFs should be completed.

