6.2.2 Safety

The analysis visit windows for safety endpoints are defined as follows (note that not all safety endpoints are collected at each visit):

Table 6-3 Safety Analysis Visit Definitions

Analysis Phase	Analysis Visit (Derived)	Study Visit (eCRF)	Window
Pretreatment	Baseline	Day 1/Visit 2	Treatment Day ≤ 1

Analysis Phase	Analysis Visit (Derived)	Study Visit (eCRF)	Window
Treatment	Week 1	Day 8/Visit 3	Treatment Day [6, 11]
	Week 2	Day 15/Visit 4	Treatment Day [12, 21]
	Week 4	Day 29/Visit 5	Treatment Day [22, 42]
	Week 8	Day 57/Visit 6	Treatment Day [43, 70]
	Week 12	Day 85/Visit 7	Treatment Day [71, last dose + 14
			days]

Local dermal tolerability data will be collected both pre-dose and post-dose at day 1 (visit 2)

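### SAP Table 5-15 can omit some unscheduled and early-exit local-tolerability ratings, and its early-exit time point has no matching window in Table 6-3

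*SAP*

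**What the plan says.** **Selection.** Under SAP 6.2, "if there are multiple valid measurements within the same analysis window, the one closest to the target day of the visit will be used". Ties go to the later value: "If multiple valid scores are equidistant from the target day of the visit, the latter observation will be used to represent the analysis window". This is a default that holds unless the SAP says otherwise, and neither 6.2.2 nor 5.1.1.5.4 makes an exception for local tolerability. Section 6.2 adds: "All assessments will be included in respective listings".

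**Windows.** In SAP Table 6-3 the baseline window is "Treatment Day ≤ 1" and the next is "Treatment Day [6, 11" (Days 6 to 11). The later windows are contiguous: 12-21, 22-42, 43-70, and then Week 12, given as "Treatment Day [71, last dose + 14" days.

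**Table.** SAP Table 5-15 is described as "Summary by parameter and analysis visit". Its time points are pre-dose and post-dose on Day 1, Weeks 1, 2, 4 and 8, and Week 12/early exit. It is produced in total and by cohort and has no worst post-baseline row. A footnote says all local tolerability data are listed.

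**Collection.** Protocol Table 1 and 8.4.5 require a tolerability rating at the Week 12/Early Exit visit. At unscheduled visits (Protocol 6.3.3) adverse events must be assessed; beyond that, "Additional evaluations should be performed as necessary, and the appropriate eCRFs should be completed". Protocol 5.4.2 makes unacceptable dermal tolerability a ground for discontinuing treatment.

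**The concern.** The rule chooses between ratings by calendar distance alone. That is reasonable for efficacy. For tolerability, a visit can fall off schedule because of the reaction itself, and that is the rating the rule tends to set aside when a routine visit sits nearer the target.

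An example: a child is graded 0 for stinging/burning at Visit 5 on Day 29 and exits on Day 38 with grade 3. Both ratings fall in Days 22-42. The distances from the target are 0 and 9 days, so assignment by day puts the 0 in Table 5-15 and leaves the 3 out. A rating on Day 4 has no analysis visit at all.

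Safety and tolerability form the first study objective and there is no control group, so the grade distribution in Table 5-15 carries much of the tolerability message. The PK cohort, with at least 16 evaluable children, is summarised separately, and there one or two missing grades would change a percentage visibly.

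**Working it through.** **1. The plan's own figure.** Protocol 4.1 gives about 100 patients and 15% attrition. 100 × (1 − 0.15) = 85, which matches the stated completers and leaves about 15 early exits.

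**2. Rule applied.** Let t be the window target (Days 8, 15, 29, 57, 85). An exit rating on day d is tabulated if d lies in a window and no earlier visit v in that window has |v − t| < |d − t|. A tie keeps the exit rating, because it is the later one. All visits before the exit are taken as attended, and exits are assigned by day, as Table 6-3 reads.

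**3. Visits exactly on target, exit on Days 2-84 (83 days).**

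| Window | Exit days not tabulated | Count |
|---|---|---|
| none | 2-5 | 4 |
| Week 1 (6-11) | 9-11 | 3 |
| Week 2 (12-21) | 16-21 | 6 |
| Week 4 (22-42) | 30-42 | 13 |
| Week 8 (43-70) | 58-70 | 13 |
| Week 12 (from 71) | none before Day 85 | 0 |
| **Total** | | **39** |

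39/83 = 47% are not tabulated and 44/83 = 53% are.

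**4. Visits off target.**
- Visit days drawn uniformly within the protocol windows (200,000 draws): 4.8% have no window and 30.0% lose to a closer rating, about 35% in all.
- Every visit at the early edge (Days 8, 12, 22, 50, 78): 4 + 3 + 3 + 6 + 6 = 22 days. That is 22/78 = 28% leaving out the visit days themselves, or 22/83 = 27% counting them as tabulated.
- Every visit at the late edge (Days 10, 18, 36, 64, 92): 4 + 1 + 3 + 6 + 6 = 20 days, so 20/79 = 25%, or 20/83 = 24%.

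**5. Scaled to about 15 exits.** 0.47 × 15 = 7.1; 0.35 × 15 = 5.3; 0.28 × 15 = 4.2; 0.25 × 15 = 3.8. Roughly 4 to 7 exit ratings are left out if exit days are even over Days 2-84 and each exit has a rating. The documents state neither condition.

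**6. The other reading.** If every exit rating goes to the Week 12/early-exit row of Table 5-15 whatever its day, none of these is lost. The two tables support different answers.

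**7. Unscheduled ratings.** Take one extra rating in a child who attends every visit. With on-target visits it is not tabulated on 79 of 83 days (95%): 4 with no window and 75 that lose to the scheduled visit. With spread visits the figure is about 69%, and at the window edges about 49% (38/78 or 39/79). When an unscheduled rating is closer to target, it displaces the routine one. Reading 6 does not help here.

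**8. Closing the gap alone.** Starting Week 1 at Day 2 removes the 4 days without a window. With on-target visits, exit ratings still lose on 35 of 83 days (42%) and unscheduled ratings on 79 of 83.

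**The case against.** The strongest reply is that bad reactions have another route into the tables. Protocol 12.1 requires a clinically significant local sign or symptom to go on the adverse event form, and 6.3.4 does the same for anything the investigator judges an adverse event. SAP Table 5-13 tabulates TEAEs by worst severity, treatment-related TEAEs, and TEAEs leading to study discontinuation, none of them by visit window. A reaction bad enough to end participation should appear there. This stands. A reader might infer that severe burning at a Day 38 exit, or irritation at a Day 4 exit, would be seen only in a listing, but the documents do not support that. What can go missing is the 0-3 grade from Table 5-15. The adverse event tables are not a full substitute: entry depends on judgement, and Protocol 9.1.3 grades severity by interference with activity, a different scale.

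Second, a reader might infer that ratings vanish from every by-visit safety table, or that most exit ratings are lost. Local tolerability sits in one table; the other by-visit safety table is vital signs. Over Days 2-84 most exit ratings are kept in every scenario tried. Stopping the count at Day 70 gives 39/69 = 57%, but leaves out Days 71-84, when none is lost.

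Third, the early-exit label in Table 5-15 may mean that exits are kept. That is possible, since the protocol makes Early Exit part of Visit 7. But Table 6-3 assigns by day and starts Week 12 at Day 71, so two programmers could build different tables.

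Finally, no scheduled visit falls on Days 2-5, tolerability need not be rated at an unscheduled visit, attrition covers all causes, and no intolerance rate is given. All of this is correct, and it limits what can be said about the size of any bias.

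**Conclusion.** Table 5-15 can omit some unscheduled and early-exit tolerability ratings: any on Days 2-5, and any that lose to a rating closer to target. Placement of an exit rating before Day 71 is ambiguous between Tables 5-15 and 6-3. Assigned by day, about 25% to 47% of exit days over Days 2-84 are not tabulated, or roughly 4 to 7 of about 15 exits, on the assumptions in the working; placed in the early-exit row, none is. For unscheduled ratings the loss is larger, about 49% to 95% of days, but how many such ratings will exist is unknown.

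The direction of any bias is inferred. Since intolerance is a ground for stopping, omitted exit ratings may be worse than average, which would tilt Table 5-15 towards good tolerability. The documents hold no data to confirm this, and the same rule also drops mild ratings. The listings and the adverse event tables limit the consequence. The point is still worth settling in the SAP, because nothing else summarises these grades.

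**What to change.** Three changes to the SAP:

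1. In Table 6-3, start the Week 1 safety window at Day 2, giving Days 2 to 11.
2. In Table 6-3, state how a tolerability rating at an early exit before Day 71 is assigned, so that it agrees with the Week 12/early-exit time point in Table 5-15.
3. In Table 5-15, add the worst post-baseline grade for each parameter over all scheduled, unscheduled and exit ratings, in total and by cohort. Say whether the Day 1 post-dose rating counts.

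Keep closest-to-target for the by-visit rows and for efficacy. Taking the highest grade within each window instead would be more debatable: it turns a status-by-visit table into a maximum that tends to rise with the number of ratings, over windows of very different length. The separate row recovers every rating without that side effect.

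The cost is a few lines of SAP text and one extra summary to program. Reported tolerability may look slightly less favourable.
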